## AMENDMENT SUMMARY

Version	Date	Description
1.0	09-Apr-2018	Initial release
2.0	18-May-2018	
Amendment 1. The protocol was amended based on feedback from Health Canada on contraception use for male subjects and dose escalation stopping rules. Minor clarifications were also incorporated into the protocol. Details of all changes and the rationale are provided in Section 12.1.

3.0	10-Sep-2018	
Amendment 2. The dose escalation scheme in Part A was amended to allow an incremental increase in the dose of nalbuphine based on a percentage of up to 50% from the last dose (rather than an absolute 27 mg dose increase), if supported by the safety data of the preceding cohorts up to a 2-3-fold the therapeutic dose. Doses of nalbuphine are not to exceed 486 mg (ie, 3-fold the therapeutic dose).
 
The amendment is proposed based on the preliminary safety results of the first 4 cohorts indicating a lower than expected incidence of adverse events and mildness (all Grade 1 except for 1 event of Grade 2 nausea) of the adverse event profile up to a dose of 162 mg nalbuphine.
 
Any episode of vomiting (instead of Grade 2 or higher) will be considered as a possible signal of intolerance in the evaluation of the maximum safe dose. In addition, an option to use both pharmacokinetic and safety data to identify the maximum safe dose was included.
 
Additional protocol clarifications were also added regarding urine drug screens, the statistical analyses of the pharmacodynamic data in Part B, and data listings of the Columbia-Suicide Severity Rating Scale.
 
Details of all changes and the rationale are provided in Section 12.2.

## **ACRONYMS & ABBREVIATIONS**

AE	adverse event
ALT	alanine aminotransferase
Alu	aluminum
AST	aspartate aminotransferase
AUC	area under the curve
$AUC_{0-\infty}$ or $AUC_{\infty}$	area under the plasma drug concentration time curve extrapolated to infinity
$AUC_{\text{last}}$	area under the plasma drug concentration time curve from the time of dosing to the last measurable concentration
BID	2 times daily
BLQ	below the limit of quantification
BMI	body mass index
bpm	beats per minute
CI	confidence interval
CL/F	apparent clearance
$C_{\max}$	maximum observed plasma drug concentration
CNS	central nervous system
COWS	Clinical Opiate Withdrawal Scale
CRF	case report form (electronic or paper)
CRU	clinical research unit
C-SSRS	Columbia-Suicide Severity Rating Scale
CSR	clinical study report
CTCAE	Common Terminology Criteria for Adverse Events
CV	coefficient of variation
DAT	divided attention test
DRC	Data Review Committee
DSM-IV-TR	Diagnostic and Statistical Manual of Mental Disorders – Fourth Edition – Text

	Revision
DSST	digit symbol substitution test
ECG	electrocardiogram
EDC	electronic data capture
$E_{\max}$	maximum effect
$E_{\min}$	minimum effect
ER	extended-release
FDA	Food and Drug Administration
FSH	follicle-stimulating hormone
GCP	Good Clinical Practice
HAP	human abuse potential
HCl	hydrochloride
HIV	human immunodeficiency virus
IB	Investigator's Brochure
ICF	informed consent form
ICH	International Conference on Harmonisation
IR	immediate release
IRB	Institutional Review Board
IV	intravenous
kel	first-order elimination rate constant
MedDRA	Medical Dictionary for Regulatory Activities
MPC	maximum pupil constriction
MSD	Maximum Safe Dose
PD	pharmacodynamics
PK	pharmacokinetics
Q1	first quartile
Q3	third quartile
QD	once per day

RMS	root mean square
SAE	serious adverse event
SAP	statistical analysis plan
SD	standard deviation
SE	standard error
SpO 2	blood oxygen saturation
SSTM	Sternberg short-term memory test
t ½	elimination half-life
TA_AUE	time-averaged area under the effect curve
TA_PAOC	time-averaged pupillometry area over the curve
TBD	to be determined
TEAE	treatment-emergent adverse event
TE max	time to maximum effect
TE min	time to minimum effect
T max	time to maximum observed plasma drug concentration
TMPC	time to maximum pupil constriction
THC	tetrahydrocannabinol
VAS	visual analog scale
Vd/F	apparent volume of distribution

## 1. STUDY BACKGROUND

Nalbuphine is a derivative of 14-hydroxymorphine and is structurally related to the opioid  $\mu$ -receptor agonist oxymorphone and the opioid  $\mu$ -receptor antagonist naloxone. Nalbuphine is a competitive antagonist of the  $\mu$ -opioid receptor while producing agonist effects at the  $\kappa$ -opioid receptor and is therefore classified as an 'opioid agonist-antagonist'. Unlike morphine and other potent mu-agonists, nalbuphine produces an agonist-antagonist "ceiling effect" and does not produce a dose-dependent increase in respiratory depression as the dose is increased.

In the US, nalbuphine was approved in 1979 as nalbuphine hydrochloride (HCl) for injection (originally marketed as Nubain®) and is medically indicated to treat moderate to severe pain, a supplement to balanced anesthesia, for pre-operative and post-operative analgesia and obstetrical analgesia during labor and delivery. No oral formulations of nalbuphine have been approved for any indication; the drug is available only in generic, parenteral formulations. Presently, nalbuphine is not a controlled substance under the Controlled Substances Act (CSA; 21 U.S.C. 812) in the US and is a Schedule IV controlled drug substance under the Controlled Drugs and Substances Act in Canada.

Trevi Therapeutics, Inc. is developing an oral, extended-release (ER) tablet formulation of nalbuphine. Nalbuphine has not been studied in an oral abuse potential study. From the literature, the abuse potential of parenteral formulations of nalbuphine has been evaluated in dependent and non-dependent opioid users and results from some of these studies showed that nalbuphine produced abuse-related positive subjective responses that were similar to those of the opioid, morphine. In a randomized, placebo-controlled, double-blind, crossover trial, 16 healthy volunteers not dependent on opioids received injections of 2.5, 5.0 or 10 mg/70 kg nalbuphine, 10 mg/70 kg morphine, or saline over a 15-second interval. Subjective and objective measures were tested between 5 and 300 minutes post-injection. The results demonstrated that the administration of nalbuphine produced dose-related effects on subjective, psychomotor and physiological variables. The profiles of subjective and physiological responses were similar between the 10 mg/70 kg doses of nalbuphine and morphine: both produced statistically significant ( $P < 0.001$ ) differences in subjective effects (eg, drug liking), pupil constriction, and induced impaired psychomotor performance (number of digit symbols drawn) when compared to saline. In another study conducted in 8 subjects not dependent on opioids and with a history of opioid abuse, parenteral doses of 8 mg/70 kg nalbuphine produced pupil constriction comparable to 10 mg/70 kg morphine; however, increasing the dose of nalbuphine up to 72 mg/70 kg (a nine-fold dose increase) did not result in a dose-dependent increase in pupil constriction (equivalent higher doses of morphine were not tested).

One (1) study (NAL 20) evaluated opiate withdrawal-related effects in subjects with osteoarthritis after administration of nalbuphine ER tablets for 21 days followed by abrupt study drug discontinuation. The objective opiate withdrawal scale (OOWS) scores obtained from the study showed an absence of any physical withdrawal symptoms in most active arm subjects scored (85% of subjects scored) or minimal evidence of physical withdrawal symptoms.

Nalbuphine was well absorbed following oral administration of nalbuphine ER tablets in healthy volunteers. The median time of observed peak concentrations ( $T_{max}$ ) was 3 to 6 hours after oral doses of up to 162 mg nalbuphine ER tablets, while the median  $T_{max}$  of nalbuphine was 0.5 hours after oral administration of 54 mg nalbuphine as a solution (Nubain®) (equivalent to 60 mg nalbuphine HCl solution). Exposure (area under the curve; AUC) of nalbuphine after single dose administration of Nalbuphine ER tablet and oral solution was shown to be comparable with a relative bioavailability of 94% under fasting conditions. However, as expected, the rate of absorption for the ER tablet is slower than the rate of the oral solution with a reduced maximum observed plasma drug concentration ( $C_{max}$ ) and delayed  $T_{max}$  (5.8 hours compared to 0.5 hours, respectively), which would be expected from the ER mechanism of this formulation.

Coadministration of nalbuphine ER tablets with a high caloric meal did not affect  $T_{max}$  but  $C_{max}$  values were approximately 1.5-fold higher compared to dosing under fasting conditions (Study NAL 06). However when administered as a nalbuphine solution, the food effect was less pronounced with an 11% decrease in  $C_{max}$  and approximately 24% increase in AUC under fed relative to fasting conditions.

The mean elimination half-life ( $t_{1/2}$ ) of nalbuphine varied between 6.6 and 9.6 hours across clinical studies. Nalbuphine is metabolized by the liver, possibly undergoes enterohepatic circulation, and is excreted via the kidneys. Nalbuphine metabolites are reported to be pharmacologically inactive.

Following a single oral dose, nalbuphine exposure was dose-dependent and increased with increasing dose in a near dose proportional manner in healthy subjects. The mean exposure of nalbuphine ranged between 4.13 to 21.6 ng/mL and 58.8 to 328 ng.hr/mL for  $C_{max}$  and the area under the curve extrapolated to infinity ( $AUC_{0-inf}$ ), respectively, over the 27 mg to 162 mg dose range. Drug exposure in healthy female subjects was consistently higher (~ 1.3-1.6 fold at the 162 mg dose) than that in male subjects; however, the differences were not statistically significant ( $P$  value > 0.05) (Study NAL07). The  $t_{1/2}$  was similar between males (8 to 9 hours) and females (7 to 11 hours), and was independent of dose and gender. In an open-label multiple escalating dose study of nalbuphine ER (TR01), 15 hemodialysis patients with pruritus and 9-matched healthy subjects were evaluated. Subjects were titrated every 3-4 days from 27 mg once per day (QD) on Day 1 to 27 mg 2 times daily (BID) then 54 mg BID, 108 mg BID and finally 162 mg BID over a 13-day period. Exposure ( $C_{max}$  and are under the curve over the dosing interval [ $AUC_{tau}$ ]) increased in a dose proportional fashion over the 27-mg to 162-mg BID dose range: 2-, 4-, and 6-fold increases in dose resulted in approximately 2-, 5-, and 6-fold increases, respectively, in mean  $C_{max}$ , and  $AUC_{tau}$ .

## 1.2 Study Rationale

Nalbuphine is an opioid agonist-antagonist and produces effects related to the central nervous system (CNS). Drug products with CNS activity are associated with abuse potential. Therefore, this protocol will evaluate the abuse potential, as well as the pharmacokinetics (PK) and safety, of nalbuphine solution and intact ER tablets administered orally in non-dependent, recreational opioid users. The abuse potential of nalbuphine will be evaluated against placebo and the  $\mu$ -agonist opioid analgesic hydromorphone HCl solution administered orally. The active drugs (ie, nalbuphine and hydromorphone) will be administered as solutions in order to maximize the peak exposure ( $C_{max}$ ). As described in the Food and Drug Administration (FDA) Guidance for Industry, the assessment of abuse potential requires the examination of doses ranging from minimally effective to supratherapeutic; however, a maximum (supratherapeutic) dose of nalbuphine that can be safely administered in a healthy population has not been identified. Therefore, this study will include a Dose Selection Study (Part A) in order to identify the appropriate doses of nalbuphine to administer in the Main Study (Part B).

## 2. STUDY OBJECTIVES AND ENDPOINTS

### 2.1 Study Objectives

The primary and secondary study objectives will be addressed in the Main Study (Part B). The exploratory objectives will be addressed in the Dose Selection Study (Part A).

### **2.1.1 Primary Objective**

The primary objective of the Main Study is to evaluate the abuse potential of orally administered nalbuphine solution and nalbuphine ER intact tablets relative to hydromorphone solution (the active comparator) and placebo in non-dependent, recreational opioid users.

### **2.1.2 Secondary Objectives**

The secondary objectives of the Main Study are:

- To assess the cognitive and psychomotor effects of orally administered nalbuphine solution and nalbuphine ER intact tablets relative to hydromorphone solution and placebo in non-dependent, recreational opioid users.
- To assess the PK of orally-administered nalbuphine solution and nalbuphine ER tablets in non-dependent, recreational opioid users.
- To assess the safety and tolerability of orally-administered nalbuphine solution and nalbuphine ER tablets relative to hydromorphone solution and placebo in non-dependent, recreational opioid users.

### **2.1.3 Exploratory Objectives**

The exploratory objectives that will be evaluated in the Dose Selection Study are:

- To assess the safety and tolerability of various doses of orally-administered nalbuphine solution and determine the maximum safe dose (MSD) in non-dependent, recreational opioid users.
- To assess the PK and pharmacodynamics (PD; pupillometry) of various doses of orally-administered nalbuphine solution in non-dependent, recreational opioid users.

## **2.2 Endpoints**

### **2.2.1 Primary Endpoint**

The primary endpoint for the Main Study is the peak (maximum) effect ( $E_{max}$ ) for Drug Liking (“at this moment”), assessed on a bipolar, 0 to 100 point visual analog scale (VAS).

### **2.2.2 Key Secondary Endpoints**

The key secondary endpoints for the Main Study are the following measures of global effects:

- Overall Drug Liking VAS ( $E_{max}$  and peak minimum effect [ $E_{min}$ ])
- Take Drug Again VAS ( $E_{max}$ )

### **2.2.3 Other Secondary Endpoints**

The other secondary endpoints for the Main Study are described below.

### 2.2.3.1 Pharmacodynamic Endpoints

- Balance of effects:
  - Drug Liking VAS ( $E_{\min}$ , time to maximum/minimum effect [ $TE_{\max}/TE_{\min}$ ], and time-averaged area under the effect curve [TA\_AUE])
- Positive drug effects:
  - High VAS ( $E_{\max}$ ,  $TE_{\max}$ , and TA\_AUE)
  - Good Drug Effects VAS ( $E_{\max}$ ,  $TE_{\max}$ , and TA\_AUE)
- Negative drug effects:
  - Bad Drug Effects VAS ( $E_{\max}$ ,  $TE_{\max}$ , and TA\_AUE)
- Other effects:
  - Hallucination VAS ( $E_{\max}$ ,  $TE_{\max}$ , and TA\_AUE)
  - Any Drug Effects ( $E_{\max}$ ,  $TE_{\max}$ , and TA\_AUE)
  - Drowsiness/Alertness VAS ( $E_{\min}$ ,  $TE_{\min}$  and TA\_AUE)
  - Bowdle VAS ( $E_{\max}$ ,  $TE_{\max}$ , and TA\_AUE)
  - Drug Similarity VAS (score at 12 hours)
- Objective measure:
  - Pupillometry (maximum pupil constriction [MPC], time to MPC [TMPC], and time-averaged pupillometry area over the curve [TA\_PAOC])
- Cognitive and psychomotor effects:
  - Divided Attention Test (DAT)
    - Root mean square (RMS) distance: the RMS distance from the center of the road (pixels) ( $E_{\max}$ )
    - Percentage over road: percentage of time over the road (%); ( $E_{\min}$ )
    - Greatest distance: the maximum distance from the center of the road (pixels) ( $E_{\max}$ )
    - Response latency of correct responses (msec) ( $E_{\max}$ )
    - Average number of false alarms ( $E_{\max}$ )
    - Percentage of target hits (%) ( $E_{\min}$ )
  - Digit Symbol Substitution Test (DSST)
    - Number of symbols completed ( $E_{\min}$ )
    - Number of errors (symbols completed incorrectly) ( $E_{\max}$ )

- Sternberg Short-Term Memory Test (SSTM)
  - d'Prime (d') pooled, for all valid responses ( $E_{min}$ )
  - Mean reaction time pooled, for all valid responses ( $E_{max}$ )

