### 6.1.1 Visual Analog Scale

Table 10 shows the VAS items administered in this study. Each VAS is scored as an integer from 0 to 100. The use of a unipolar or bipolar scale is determined by the nature of the subjective effect being measured. Unipolar VASs (eg, High, Good Drug Effects, Bad Drug Effects, Any Drug Effects, and Hallucinations) are presented with anchors such as "Not at all" (score = 0) to "Extremely" (score = 100), where the neutral point equals 0. Note that scales that refer specifically to drug (eg, Good Drug Effects, Bad Drug Effects, Any Drug Effects) are not administered pre-dose. When appropriate, VASs will be administered as bipolar measures, meaning that the neutral point equals 50 (eg, Drug Liking, Overall Drug Liking, Take drug Again, and Drowsiness/Alertness VAS). The neutral point will also be labeled with an anchor, such as "neither like nor dislike".

Eligible subjects who appear to have difficulty differentiating between bipolar and unipolar scales (eg, making errors such as selecting 50 as neutral for a unipolar scale) during the

Qualification Phase will undergo additional practice training on the difference between the scale types.

[figure not shown]

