**Table 10 Description of Subjective Effects Visual Analog Scales**

Scale Interpretation	Exclude Pre-dose	Description	Question Text	Response Anchors
Balance	Yes	Drug Liking	At this moment, my liking for this drug is	0: Strong disliking 50: Neither like nor dislike 100: Strong liking
Global	Yes	Overall Drug Liking	Overall, my liking for this drug is	0: Definitely not 50: Neutral 100: Definitely so
Global	Yes	Take Drug Again	I would take this drug again	0: Definitely not 50: Neutral 100: Definitely so
Positive	Yes	Good Drug Effects	At this moment, I feel good drug effects	
Positive	No	High	At this moment, I feel high	0: Not at all
Negative	Yes	Bad Drug Effects	At this moment, I feel bad drug effects	
Other effects	No	Hallucinations	I am experiencing hallucinations	100: Extremely
Other effects	Yes	Any Drug Effects	At this moment, I feel any drug effect	
Other effects	No	Drowsiness/Alertness	At this moment, my mental state is	0: Very drowsy 50: Neither drowsy nor alert 100: Very alert

Scales have 5 possible interpretations: (1) "Positive" subjective effects, (2) "Negative" subjective effects, (3) the "Balance" between positive and negative effects, (4) "Other effects" (ie, pharmacologic effects that indicate an active substance, which may be perceived as either positive or negative depending on the context), and (5) "Global" (ie, end-of-day assessment or next day overall assessment).

The overall appearance of all VAS items is similar to the screen images below. [Figure 3A](#) presents the display for a typical question. Using a mouse, the subject must position the cursor over the small vertical box (a "slider") and click on it to move it left or right. To register the response, the subject must then press the "OK" button that appears below the horizontal line ([Figure 3B](#)). This multi-step procedure was designed to reduce the possibility of either accidental or automatic responding to such scales. The questions and anchors will be modified appropriately to reflect study-specific questions.

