#### 6.1.5 Pupillometry

Pupillometry will be used as an objective physiological PD measure as it is a sensitive measure of central opioid/stimulant action and appears to be resistant to tolerance development with repeated administration. An electronic pupillometer (NeuroOptics) will be used to measure pupil diameter. Data from a series of frames will be used in the calculation, and the final display will show the weighted average and standard deviation (SD) of the pupil size. Measurements will be collected under mesopic lighting conditions. For each subject, every effort will be made to use the same eye for all assessments throughout the study.

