#### 6.4 Appropriateness of Measures

The selected PD measures will assess positive and negative subjective drug effects associated with the abuse potential of a drug, as well as objective measures evaluating the cognitive and opiate effects. A number of concurrent measures will be used in this study to assess the abuse potential of nalbuphine relative to hydromorphone and placebo. These measures are grouped as follows:

- Measures of balance of effects (eg, rating of "at the moment" drug liking)
- Measures of global effects (eg, willingness to take the drug again)
- Measures of positive effects (eg, good effects, high)
- Measures of negative effects (eg, bad effects)
- Measures of stimulant and sedative effects (eg, drowsiness/alertness)
- Measures of perceptual disturbances (eg, hallucinations, Bowdle VAS)
- Measures of cognitive effects (eg, DAT, DSST, SSTM)
- Measure of opiate effect (eg, pupil size)

The selection of subjective abuse potential measures in this study, including the use of a bipolar Drug Liking VAS as the primary endpoint, is consistent with regulatory and literature guidelines. The assessment of drug liking has been chosen as the primary measure in the current study because the degree of subject liking is considered one of the most sensitive indices of abuse liability. The Drug Liking VAS and the Overall Drug Liking VAS assess slightly different aspects of drug liking. Drug Liking VAS assesses the subject's liking of the drug at the moment the question is asked, may be less subject to recall bias, and is useful for understanding the time-course of the effects. The Overall Drug Liking VAS is thought to assess 'global' drug effects (ie, subjective effects over the whole course of the experience including any carry-over effects), and has the additional advantage that the subject is generally sober by the time of the assessment (ie, end of day and/or next day). Other VAS items will measure positive, negative, and other subjective effects to assess the pharmacologic response to the study drugs. The Take Drug Again VAS will provide a global measure of drug effects and indicate the subject's willingness to take the drug again.

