$$H_0: \mu_T - \mu_P \geq 11 \text{ versus } H_a: \mu_T - \mu_P < 11$$

where,  $\mu_T$  is the mean for nalbuphine and  $\mu_P$  is the mean for placebo and will be applied to the following contrasts:

- Treatment D: Nalbuphine *low dose* versus Treatment A: Placebo
- Treatment E: Nalbuphine *intermediate dose* versus Treatment A: Placebo
- Treatment F: Nalbuphine *high dose* versus Treatment A: Placebo
- Treatment G: Nalbuphine 162 mg ER intact versus Treatment A: Placebo

No clinically meaningful differences have been defined for any of the other PD measures and thus, assigning a  $\delta$  margin is not applicable. Furthermore, changes observed on measures of cognition or performance do not inherently imply that the drug has abuse potential, but rather provide important information related to the drug's CNS pharmacology. For PD endpoints that have not been defined as primary or key secondary, the following 3 hypotheses will be used to provide information on the relative abuse potential of the test drug in humans:

1.  $H_0: \mu_C - \mu_P = 0$  versus  $H_a: \mu_C - \mu_P \neq 0$
2.  $H_0: \mu_C - \mu_T = 0$  versus  $H_a: \mu_C - \mu_T \neq 0$
3.  $H_0: \mu_T - \mu_P = 0$  versus  $H_a: \mu_T - \mu_P \neq 0$

A significance level of 0.05 will be used for all individual one-sided and two-sided hypothesis tests. Multiple comparison adjustments will not be made.

The abuse potential of nalbuphine will be assessed through evaluation and integrative interpretation of the pattern of results across the various types of measures: measures of positive response (ie, measures most predictive of the drug's abuse potential and reinforcing properties), measures of negative response (ie, measures that potentially mitigate against abuse potential), measures of stimulant effects, measures of other effects and measures of cognitive and psychomotor effects. The treatment comparisons will support evaluation of the importance of the steepness of the dose-response curves and the similarity of responses to nalbuphine, as compared to the responses to hydromorphone and placebo.

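### Section 8.1.3 will interpret stimulant effects, but the Drowsiness/Alertness VAS, the measure Section 6.4 names for them, has a peak endpoint only in the drowsy direction

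*Protocol*

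**What the plan says.** Four parts of the protocol bear on this, all for Part B.

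- **The scale.** Table 10 anchors it as "0: Very drowsy 50: Neither drowsy nor alert 100: Very alert". Section 6.1.1 lists it among the bipolar scales with a neutral point of 50. High scores are the alert direction and low scores the drowsy direction.
- **Its role.** Section 6.4 groups the measures by what they assess and has a line for "Measures of stimulant and sedative effects (eg, drowsiness/alertness". No other scale is named on that line.
- **Its use.** The closing text of Section 8.1.3, before the sensitivity analysis, says abuse potential will be judged from the pattern across several types of measure, including "measures of stimulant effects, measures of other effects and measures of cognitive and psychomotor effects".
- **Its endpoints.** Section 2.2.3.1, under other effects, gives "Drowsiness/Alertness VAS ( $E_{\min}$ , $TE_{\min}$ and TA\_AUE". Neither document assigns an Emax or TEmax to this scale.

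Section 8.1.3 also plans descriptive statistics at each time point. It models Emax, Emin and TA_AUE as appropriate, with two-sided tests at 0.05 for endpoints that are neither primary nor key secondary. The SAP covers Part A only. Its Section 9 repeats the sentence on stimulant effects, and its Appendix A defines Emax and TEmax in general terms, but it adds no endpoint for this scale.

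**The concern.** Emin records the drowsiest reading of the session. A drug that makes subjects more alert for a few hours and then lets them return to neutral leaves that reading roughly where it was. TA_AUE does respond to alertness, but it spreads a short effect over 24 h and nets it against any later drowsiness. The plan therefore has a sharp endpoint for the direction that the integrated judgement does not name, and only a blunt one for the direction that it does name.

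What is at stake is the reading of a null result. If the report finds no stimulant effect on this scale, a reader could not tell whether the drug has none or whether the listed endpoints were insensitive to it. This applies to the hydromorphone-placebo, hydromorphone-nalbuphine and nalbuphine-placebo comparisons alike.

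**Working it through.** The plan states no figure for this scale, so there is nothing to reproduce. The check applies the listed parameters to assumed score profiles on the Part B schedule.

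**Inputs from the documents.** Protocol Table 3 records the scale pre-dose and at 0.5, 1, 1.5, 2, 3, 4, 5, 5.5, 6, 6.5, 7, 8, 9, 12 and 24 h, which is 15 post-dose readings. Neutral is 50. TA_AUE is taken as the linear trapezoidal area from 0 to 24 h divided by 24, with pre-dose at time 0 (the trapezoidal rule is in SAP Appendix A).

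**Assumed profiles.** *Alert only:* the score rises linearly from 50 at 0 h to 50 + P at 1 h, returns to 50 at 4 h, then stays flat. *Alert then drowsy:* the same, followed by a fall to 50 − 0.8P at 5 h and recovery to 50 at 9 h.

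**Formulas.**

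- Alert phase: triangle of base 4 h and height P, area 4P/2 = 2P. Shift in TA_AUE = 2P/24. For P = 25: 50/24 = 2.08.
- Drowsy phase: triangle of base 5 h and height 0.8P, area 5 × 0.8P/2 = 2P. It cancels the alert phase exactly, by construction.

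| Profile | Emax | Emin | TA_AUE |
|---|---|---|---|
| Flat at 50 | 50 | 50 | 50.0 |
| Alert only, P = 15 | 65 | 50 | 51.25 |
| Alert only, P = 25 | 75 | 50 | 52.08 |
| Alert only, P = 40 | 90 | 50 | 53.33 |
| Alert then drowsy, P = 15 | 65 | 38 | 50.0 |
| Alert then drowsy, P = 25 | 75 | 30 | 50.0 |
| Alert then drowsy, P = 40 | 90 | 18 | 50.0 |

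Part of the dilution comes from the schedule. The interval from 12 to 24 h carries (24 − 12)/24 = 50% of the average and rests on two readings.

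**Illustrative power.** The documents give no variability for this scale, so every input here except the 42 completers and the Table 3 times is assumed: period-level SD 8, per-reading SD 8 to 12, an alerting effect held from 0.5 to 4 h, and a paired t-test at two-sided 0.05.

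| Endpoint and assumed daily pattern | +10 points | +15 points |
|---|---|---|
| Emin, with or without a 15-point dip at 12 h | 6–16% | 5–24% |
| TA_AUE | 13–16% | 24–30% |
| Emax, no natural rise at 24 h | 69–93% | about 99% or more |
| Emax, natural 15-point rise at 24 h | 50–52% | 92–97% |
| Emax, natural 25-point rise at 24 h | 10–21% | 32–59% |

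Emin and TA_AUE are weak throughout. Emax is usually far better, but a strong next-morning rise in alertness removes most of its advantage, and at +10 points nearly all of it.

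**Could another measure supply the missing peak?**

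- *Pupillometry.* Section 6.1.5 calls it a "sensitive measure of central opioid/stimulant action", but Section 6.4 classes pupil size as an opiate effect, and its peak endpoint is maximum constriction.
- *Drug Similarity VAS.* Table 11 includes stimulants as comparators, but the endpoint is one rating at 12 h, limited to drugs the subject already knows.
- *Summaries by time point.* The maximum shown there is the highest score across subjects at one time. It is neither a per-subject peak nor a tested contrast.

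**The case against.** The strongest case against is that the endpoint follows the pharmacology. Section 1.1 reports somnolence and one serious sedation event with nalbuphine, Section 3.2.1 lists sedation for hydromorphone, and Section 4.9.2 makes somnolence a Part A stopping criterion. Nothing in the documents points to an alerting effect of either drug. Other endpoints are also one-directional: pupillometry looks for constriction, and the cognitive tests look for impairment. The sentence in Section 8.1.3 may be template text, since it also appears in the Part A SAP, where pupillometry is the only pharmacodynamic measure. This stands as a reason to rate the impact low. It does not remove the mismatch between the stated interpretation and the endpoints. Section 8.1.3 itself says that nalbuphine's effect size on the study measures is unknown.

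Three stronger readings are tempting, and the documents do not support them.

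- *That this is the plan's only stimulant measure.* Section 6.4 offers it as an example, and the Drug Similarity VAS does ask about stimulants. It is the only measure named there, no more.
- *That the plan cannot detect a stimulant effect.* TA_AUE moves in both directions and is tested two-sided, so a large or sustained alerting effect could show. Time-point summaries could also reveal an alert phase.
- *That the protocol gives bipolar scales both extremes as a rule.* Drug Liking and Overall Drug Liking have both, but Take Drug Again is also bipolar and has Emax only.

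**Conclusion.** The point holds in a limited form. Section 8.1.3 promises an interpretation of stimulant effects, and the scale that Section 6.4 names for it has no peak endpoint in the alert direction. What remains is a diluted 24 h average and descriptive summaries. Under the assumed 25-point alert peak, the average moves by about 2 points, or not at all if an equal-area drowsy phase follows.

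The structural gap rests on the text alone. The sizes rest on assumed profiles, and the power figures also on assumed variability and daily pattern, so they are illustrative only. A reader might infer that Emax would make detection near certain; the range above shows that it would not under every daily pattern.

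The impact is low. The scale is one of many other secondary endpoints, sedation is the expected effect, and no primary or key secondary inference uses it. According to SAP Section 5, Part B had not started and was to be placed with a new site, so the change can still be made before any Part B data exist.

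**What to change.** In Section 2.2.3.1, list the Drowsiness/Alertness VAS with Emax, Emin, TEmax, TEmin and TA_AUE. In Section 8.1.3, analyse Emax with the model and two-sided hypotheses already used for the other secondary pharmacodynamic endpoints, and state that Emax is read as the alerting direction and Emin as the sedative direction.

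No new reading, visit or subject is needed. The cost is wording in two sections, extra output, and one more tested secondary endpoint. Emax adds 2 hydromorphone-placebo, 8 hydromorphone-nalbuphine and 4 nalbuphine-placebo contrasts, 14 in all. Section 8.1.3 makes no multiplicity adjustment, so 14 × 0.05 = 0.7 false positives would be expected if all 14 null hypotheses were true. The report should read these contrasts with that in mind.

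If the sponsor does not want the extra endpoint, the alternative is to remove stimulant effects from the list in Section 8.1.3, so that the plan does not promise an interpretation for which it has no peak endpoint.
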